Our objective of this study is to determine whether exercise training via neuromuscular electrical stimulation (NMES) has beneficial effects on skeletal muscle size and function in cancer patients. We hypothesize that NMES will improve skeletal muscle size, contractile function and oxidative capacity, based on our seminal observations in cancer patients that functional disability derives, in part, from deficits in skeletal muscle contractile protein and mitochondrial content and function, as well as our preliminary data showing that NMES counters such deficits. To test this hypothesis, we propose two specific aims:

Aim 1: Determine the effect of NMES on skeletal muscle fiber size and contractile function.

We hypothesize that skeletal muscle fiber size and contractile function will be greater in cancer patients receiving treatment who are randomized to NMES compared to controls.

Aim 2: Determine the effect of NMES on skeletal muscle mitochondrial content and function.

We hypothesize that skeletal muscle mitochondrial content and function will be greater in cancer patients receiving treatment randomized to NMES compared to controls.

Study Design:

We will use a prospective, randomized controlled design, in which recently-diagnosed, breast cancer patients (40 to 75 yrs) will be recruited (see Appendices I-VI for recruitment materials/data collection sheets) and undergo Baseline Testing during the 1st cycle of neoadjuvant or adjuvant chemotherapy. Patients will then be randomized (1:1) to 8 wks of NMES or Attention control intervention (n=12/group; Treatment Phase), with stratification for age and adjuvant or neoadjuvant chemotherapy. Following completion of the intervention, they will undergo Post-intervention Testing.

Baseline testing will include assessments of single muscle fiber size and mechanical function and mitochondrial content and function, as well as whole muscle size and contractile function and walking performance. Detailed descriptions of these assessments are provided below.

Treatment Phase Volunteers randomized to both NMES and attention control groups will receive instruction to maintain or increase their physical activity according to the clinics usual standard of care. Both interventions are described below in detail.

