Post-Intervention Testing will occur in patients who complete the NMES program and controls and will include measurements identical to Baseline Testing, with post-training biopsies performed ≥ 3 d following NMES to eliminate any residual effects, per our usual protocol in other training studies that have been IRB-approved. Post-intervention testing will occur within ± 14 d from the 8 week intervention point

New methodology: Our study employs cellular and organellar level measurements of skeletal muscle structure and function. Although the methodology used in these studies is not new per se, it has not been used in the setting of exercise intervention trials in cancer patients. We feel that our approach is innovative in circumventing limitations in the detection of exercise effects at the whole body or whole muscle level due to methodological shortcomings, subjective motivation and, specific to NMES, effects on neural activation. This approach can economize the initial exploratory phase of developing new exercise modalities by more accurately characterizing the effects of such programs on those properties typically improved with exercise; namely, muscle size, contractility and oxidative function.

Procedures:

All of the procedures and interventions in this study are carried out solely for research purposes, as none are part of standard therapy/care in breast cancer patients.

Primary outcomes include: skeletal muscle fiber cross-sectional area (CSA) and function and mitochondrial content, morphology and function. Secondary outcomes include: whole muscle size/function and 6 min walk performance and indices of chemotherapy-induced peripheral neuropathy (CIPN). Procedures that will be performed on volunteers to obtain these primary and secondary outcome measures are described below.

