Biopsy of the vastus lateralis (VL) will be performed, as used by our research group in a range of patient populations, including cancer patients (1), with the study leg chosen as the stronger leg in $\frac{1}{2}$ of patients and the weaker leg in the other $\frac{1}{2}$ so as not to bias adaptations based on minor functional asymmetries. Tissue will be proportioned for mechanical, immunohistochemical (IHC), mitochondrial respiratory and electron microscopy (EM) measurements, with remaining tissue frozen in liquid N₂. The VL was chosen because of its importance in determining functional disability (2) and its structural and functional deficiencies in cancer patients previously described by our laboratories (1).

Single fiber function, including tension, velocity and power, will be measured on chemically-skinned, muscle fiber segments (n \approx 25/subject/biopsy) using isotonic load clamps, as described by us (3), with data available on MHC I and IIA fibers, the two most prevalent fiber types in human muscle (1, 4).

Single fiber cross-sectional area (CSA) will be measured by IHC, as we have described (1, 3), with minor modifications to permit assessment of all MHC isoforms, as described (5).

Whole muscle contractile function will be measured, as described by us (6). Maximal peak isometric (70°, 90°) and isokinetic knee extensor torque (60 and 180°/sec) will be adjusted for thigh muscle CSA to account for variation in muscle size. Additionally, muscle fatigue will be assessed following repeated

(n=24) isometric contractions. Briefly, 24 maximal voluntary isometric contractions (2 min of intermittent contractions at 70°), following a duty ratio of 3 seconds of contraction and 2 seconds of rest. Fatigue will be defined as the average peak torque from the final 3 contractions divided by the highest peak torque achieved prior to initiation of the fatigue protocol (ie, Isometric knee extensor strength determination prior to the fatigue measure).

Thigh muscle size will be measured by dual energy x-ray absorptiometry, as described by us (1). Additionally, anthropometrics and body mass will be assessed. Height will be measured without shoes, using a stadiometer to the nearest 0.5cm. Weight will be obtained from the DEXA estimate. BMI will be calculated as weight (kg)/height(m²).

6 min walk test will be performed, as described (1), to assess changes in physical functional capacity.

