Single legged stance will be performed to test balance in each leg separately. The participants place their hands on their hips then raise the 1 foot off the floor. Stance is timed until the raised foot touches the floor, the stationary foot moves, the raised foot touches the stationary leg or the hands are taken from their starting position. It is repeated three times and the best value is used. If stance exceeds 30 seconds the test will be stopped at that time.

Accelerometry will be performed, as described (6), to monitor weight-bearing activity levels, which can be used to account for possible variation in muscle use between groups (Appendix VII).

Questionnaires (provided in Appendix VIII) will be provided to assess fatigue symptoms (Fatigue Symptom Index), physical activity level (Stanford Brief Physical Activity Questionnaire), general health/well-being (MOS SF-36) and CIPN (EORTC CIPN 20).

Nerve conduction studies (NCS) will include the sural, peroneal and tibial nerves bilaterally and are the best measure of large nerve fiber function that is affected by both exercise and chemotherapy. NCS take about ten minutes and record electrical signal after providing a very mild electrical stimulus to the skin. The amplitude, distal latency, and conduction velocity will be recorded for each nerve. Study of both legs require a total of 15-20 stimulus applications, some of which are too weak to be felt.

Clinical neuropathy assessment: The Utah Early Neuropathy Scale (UENS) is a lower extremity examination performed by a neurologist that tests different modalities of strength, sensation and reflexes to detect neuropathy. It examines great toe strength, pin sensation, allodynia, vibratory sensation and Achilles reflexes in both legs.

Treatment Phase

Volunteers randomized to both the NMES intervention and control groups will receive instruction to maintain or increase their physical activity according to the clinics usual standard of care.

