Our primary goal is to assess the effect of NMES on: single fiber tension (force/CSA), velocity and CSA and mitochondrial content and ADP-stimulated oxygen consumption rate. A general linear mixed model will be used, with treatment group as between-subject and time as within-subject effects. A random effect will be included to account for clustering of observations within subjects (ie, fibers within each subject), as described (1), with the model conceptualized as a multi-level analysis with single fiber/organellar-level outcomes comprising level 1 variables and person-level covariates comprising level 2 variables (2). Covariates (eg, stage, chemotherapeutics, and activity level) can be included in the model as level 2 variables to control for potential confounders that differ by group. Whole muscle size and function and 6 min walk performance will be used in secondary analysis to evaluate whether changes in myofilament or mitochondrial content or function scale to variation in tissue-level or whole body function or size, as we have previously observed that molecular- and organellar-level function scale to the tissue and whole-body level in cancer (3), aging (4) and chronic disease (5).

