For Aim 1, based on whole muscle results in cancer patients (3, 6), other diseased populations (7, 8) and our preliminary data, we anticipate that volunteers randomized to NMES will have greater single muscle fiber tension (20%) and CSA (20%) versus controls. We focused on these variables because they represent the two most disabling effects of cancer on muscle contractility: weakness and atrophy (3, 9). We would need $n=12$ /group to detect these differences between groups (power=90% and significance of 5%). Of note, we will likely have greater improvements in contractile velocity, per our preliminary data, which should further increase aggregate muscle power output and functionality and is readily detectable with this sample size. For Aim 2, based on our preliminary data showing the ability of NMES to improve mitochondrial content and function in the context of a profoundly atrophyic stimuli (ie, knee replacement surgery), we expect that patients randomized to NMES will have greater mitochondrial content (50%) and function (40%). Our sample size is driven by detecting changes in mitochondrial content, which would require $n=12$ /group with a power of 90% and a significance of 5%. Using this sample size, our minimal detectable differences for changes in mitochondrial function would be 14%. We have not performed sample size estimates on secondary outcomes because of the exploratory nature of these studies, but also because it is likely that we will either not be able to detect effects at this anatomic level because of confounding factors or we will detect effects at this level that are unrelated to the effects of NMES to improve skeletal muscle size and/or function (eg, enhanced neural activation related to NMES training improves whole muscle strength). This was a primary impetus

for our studies to evaluate the effects of NMES at the cellular/organellar level. However, we will evaluate these outcomes nonetheless, as they will provide important preliminary data for future trials if our hypotheses are supported by our results.

1. [name], M. J., Miller, M. S., VanBuren, P., Bedrin, N. G., LeWinter, M. M., Ades, P. A., and Palmer, B. M. (2012) Resistance training alters skeletal muscle structure and function in human heart failure: effects at the tissue, cellular and molecular levels. *J Physiol* **590**, 1243-1259
2. Hox, J. J. (2002) *Multilevel Analysis: Techniques and Applications.*, Lawrence Erlbaum Associates, Inc., Mahwah, NJ

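### The primary model names no treatment contrast and no baseline adjustment; read as group-by-time it compares raw change, which is valid but less precise than adjusting for baseline with 12 patients per group

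*Combined protocol and SAP*

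**What the plan says.** The Statistical Analysis Plan gives the primary analysis as a general linear mixed model "with treatment group as between-subject and time as within-subject effects". One random effect covers the clustering of fibers within a subject. No group-by-time term, treatment contrast, baseline covariate or common baseline mean is stated. The Aim 2 sample-size text is phrased in terms of change: "our minimal detectable differences for changes in mitochondrial function would be 14" per cent.

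Under Objectives, the Aim 1 hypothesis is a group difference: "skeletal muscle fiber size and contractile function will be greater in cancer patients receiving treatment who are randomized to NMES compared to controls". Aim 2 is worded the same way.

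Study Design randomises 1:1, 12 per group, "with stratification for age and adjuvant or neoadjuvant chemotherapy". Neither factor is named as a model term. The covariates that are named (stage, chemotherapeutics, activity level) are examples, and they "can be included in the model as level 2 variables to control for potential confounders that differ by group".

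Activity level has no stated time point. Post-intervention testing "will include measurements identical to Baseline Testing", and accelerometry under Procedures is described as something "which can be used to account for possible variation in muscle use between groups". Fiber function "will be measured on chemically-skinned, muscle fiber segments", about 25 per subject per biopsy.

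**The concern.** A group main effect would average in data taken before treatment, so the treatment effect most plausibly sits in group-by-time. With free baseline means, that term is the difference in mean change. The subject random effect does make each patient her own control, but the contrast then subtracts her baseline with a coefficient of 1, whereas regression adjustment uses a coefficient near r. The excess, (1-r) times any chance baseline gap, stays in the estimate.

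With 12 per group such gaps are not small, and the study states that its results are to support larger trials, so the size of the estimate matters as well as the p-value. The baseline value is already collected on every patient. Separately, letting covariates in according to observed group differences leaves part of the primary model to be settled after the data are seen.

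**Working it through.** **Inputs from the documents.** 12 per group, 5% significance, 90% power; expected differences 20% (tension, CSA) and 50% (mitochondrial content); detectable difference 14% (mitochondrial function); about 25 fibers per biopsy; one baseline and one follow-up biopsy. Sidedness is not stated, so two-sided is assumed. No SD or correlation is given, so r is assumed at 0.3/0.5/0.7/0.8.

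**The plan's own figure.** For 90% power with 12 per group (df 22) the noncentrality is 3.393, so the standardised difference is 3.393 × √(2/12) = 1.385. The implied SDs are 20/1.385 = 14.4%, 50/1.385 = 36.1% and 14/1.385 = 10.1%. Without a stated SD, 12 per group can be neither confirmed nor refuted.

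**Precision.** With outcome SD s, Var(change) = 2s²(1-r) and Var(adjusted) = s²(1-r²); the ratio is (1+r)/2. Suppose 12 per group gives exactly 90% on change. Simulation of 60,000 trials per r gives:

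| assumed r | variance ratio | power, change | power, adjusted |
|---|---|---|---|
| 0.3 | 0.65 | 90% | 97% |
| 0.5 | 0.75 | 90% | 95% |
| 0.7 | 0.85 | 90% | 93% |
| 0.8 | 0.90 | 90% | 91% |

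At r = 0.9 the adjusted analysis has 89.9%, so nothing is gained. If the sizing SD was instead that of the follow-up value, change has 78/90/99% and adjusted 91/95/99% at r = 0.3/0.5/0.7.

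**Chance baseline gap.** Its standard error is √(2/12) = 0.408 SD. A gap of one standard error shifts the change estimate by (1-r) × 0.408 = 0.29/0.20/0.12/0.08 SD. The detectable effect is 1.385 × √(2(1-r)) = 1.64/1.39/1.07/0.88 SD, so the shift is 17/15/11/9% of it. A gap beyond one standard error arises in about 16% of randomisations in each direction. Simulated averages over those trials:

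| | NMES starts higher | NMES starts lower |
|---|---|---|
| change estimate, % of true effect | 74/77/82/86 | 126/122/118/114 |
| power on change | 70/72/77/80% | 99/99/98/97% |
| false win for NMES, no effect (nominal 2.5%) | about 0.5% or less | 10.2/8.5/7.2/5.8% |

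When NMES starts higher, the adjusted estimate averages 100% of the effect with 97/94/91/89% power; when it starts lower, the adjusted false-win rate is 2.4 to 2.6%. Over all randomisations the change test has type I error of 4.8 to 5.1%.

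**Fibers.** With m fibers per biopsy, person-level correlation ρ and between-biopsy variance share ICC, the biopsy-mean correlation is ρ·ICC/(ICC + (1-ICC)/m). For ρ = 0.7, ICC = 0.2, m = 25 this is 0.14/0.232 = 0.60, and power on biopsy means rises from 90.1% to 94.2%. For ρ = 0.9, ICC = 0.4 it is 0.36/0.424 = 0.85, and power goes from 89.7% to 90.3%.

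These gains assume that the analysis respects the biopsy. With only a subject intercept on fiber data, the true variance of group-by-time exceeds the model's variance by the factor V/M, where V = m·ICC(1-ρ) + (1-ICC) and, for m = 25, M = (1-ICC) + [22×25/(22+48×24)]·ICC(1-ρ) = (1-ICC) + 0.468·ICC(1-ρ). Type I error is about 2Φ(-1.96/√(V/M)):

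- ρ = 0.9, ICC = 0.1: 1.15/0.905 = 1.27, giving 8%
- ρ = 0.7, ICC = 0.2: 2.30/0.828 = 2.78, giving 24%
- ρ = 0.5, ICC = 0.2: 3.30/0.847 = 3.90, giving 32%

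A common-baseline constraint alone does not cure this: in five simulated settings type I error was 20 to 41% with free baselines and still 17 to 40% with the constraint. Adjustment on patient means gave 4 to 5%.

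**Strata.** Effects that are constant over time cancel from a change contrast, and no power is lost. If the strata explain 10/20/30% of the variance of change, omitting them gives type I error of 4.0/3.0/1.9% and power of 91/92/93%, against 92/95/97% when included. After baseline adjustment they move power by -0.5 to +1.2 points.

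**Covariate rule.** In null simulations with three candidate covariates (R² of 0 to 0.2 each), a mechanical rule of adjusting when the imbalance has p<0.05 gave type I error of 3.7 to 4.8%. Free choice among all eight covariate sets gave 8 to 15%, as a worst case.

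**The case against.** The raw-change reading is an inference. The plan never writes group-by-time, does not exclude a common baseline mean, and refers to a cited paper for its random-effect structure. That stands: what the text establishes is that contrast and baseline handling are unspecified, and the single-intercept reading is likewise only the plain sense of the words. Either way a sentence is needed.

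The background sections also word the hypotheses as increases relative to control, which change answers directly. True, but under randomisation both contrasts target the same effect, so neither wording argues against the more precise one.

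A reader might infer that the planned test is biased or invalid because of baseline imbalance. The documents do not support that: at patient level the change contrast is unbiased with correct type I error, and the conditional errors offset across the two directions. Nor is it right that 32% of randomisations lose power; about 16% lose it and about 16% gain it.

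A reader might also infer that leaving out the strata is a serious error, or that on-treatment activity will be adjusted for. The covariate list is open, so the strata are not excluded, and omission is at worst conservative. Nothing says which activity measurement would be used. On-treatment activity would bias the estimate only if NMES changes activity and the variable enters a post-value model, a time interaction or a time-varying term.

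**Conclusion.** The point holds as a gap in specification and a free gain in precision. The plan should state its treatment contrast and use the baseline it already measures. On the natural reading, adjustment raises power from 90% to about 91 to 97% for assumed r between 0.8 and 0.3, with almost nothing gained at 0.85 to 0.9. It also removes a conditional error that, in about one randomisation in six in each direction, shrinks or inflates the average estimate by roughly 14 to 26%. All of this rests on assumed correlations, two-sided testing and patient-level (biopsy-mean) analysis. The strata and covariate points are minor in size and belong in the same revision. The change is worth making, but the patient-level test as read is not invalid.

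**What to change.** State the primary contrast as the NMES-versus-control difference at follow-up adjusted for the patient's own baseline value (patient-level biopsy mean as covariate), or use a longitudinal model with a common baseline mean. In either form, if fiber-level data are modelled, include a biopsy-level (patient-by-time) random term.

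Include age and adjuvant/neoadjuvant setting as fixed terms, with time interactions in the longitudinal form. Replace the rule based on observed group differences with a short prespecified list of pre-randomisation covariates. Use baseline activity only in the primary model, and keep on-treatment activity for a labelled sensitivity analysis.

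The cost is SAP wording and about 3 degrees of freedom (one for baseline, two for the strata if each is a single term), or up to about 0.5 points of power if the strata are not prognostic. No extra patients, biopsies or visits are needed.

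### The mixed model for single-fiber outcomes has a subject random effect but no biopsy-level term, so the 5% level is not assured for tension and velocity if the treatment effect is group-by-time

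*Combined protocol and SAP*

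**What the plan says.** The Statistical Analysis Plan sets up a general linear mixed model with "treatment group as between-subject and time as within-subject effects". Its one stated random effect is described thus: "A random effect will be included to account for clustering of observations within subjects (ie, fibers within each subject"). The levels are "single fiber/organellar-level outcomes comprising level 1 variables and person-level covariates comprising level 2 variables". Model details are referred to a cited earlier training study.

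Under Study Design, post-intervention testing "will include measurements identical to Baseline Testing, with post-training biopsies performed" at least 3 days after NMES, so each patient has two biopsies. Under Procedures, about 25 fibers per biopsy are tested for single-fiber function, "with data available on MHC I and IIA fibers, the two most prevalent fiber types in human muscle".

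The treatment contrast is not named. The Aim 1 hypothesis is that "skeletal muscle fiber size and contractile function will be greater in cancer patients receiving treatment who are randomized to NMES compared to controls", which reads as a between-group difference. The sample-size text says "Our sample size is driven by detecting changes in mitochondrial content", which points to change from baseline, though for Aim 2. That text plans 12 patients per group at 90% power and 5% significance.

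**The concern.** Fibers from one biopsy share whatever is particular to that biopsy: the patient's own response over the 8 weeks, the sampling site and the test day. The data therefore have three levels (fiber, biopsy, patient), while the written model has two.

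In a randomized trial with baseline and follow-up measurements, group-by-time is the natural treatment contrast. A subject intercept is common to both biopsies and cancels out of the change. Without a subject-by-time term, the model treats fibers as independent replicates of the change. The 5% level then requires that biopsy means within a patient vary no more than fiber sampling alone explains. In particular, patients must not differ in their true change. The eligibility criteria (stage I–III, neoadjuvant or adjuvant chemotherapy) and the ±14-day window for post-intervention testing give no reason to expect that.

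At stake are the p-values and confidence intervals for fiber tension and velocity, two of the five primary measures listed in the Statistical Analysis Plan. Tension is also one of the two measures on which Aim 1 is sized. CSA and mitochondrial content are affected only if several readings per biopsy enter the model. Outcomes with one value per biopsy are unaffected.

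**Working it through.** **The plan's own figure.** The 12 per group for a 20% difference cannot be reproduced, because no SD is given. Solving 12 = 2(1.96 + 1.28)²(SD/20)² gives an implied SD of about 15.1% (two-sided, normal approximation). The figure is neither confirmed nor refuted. What matters here is that it counts patients, not fibers.

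**Inputs from the documents.** 12 patients per group, 2 biopsies each, about 25 fibers per biopsy over two fiber types, 5% significance.

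**Assumptions.** The test is two-sided. Fibers per type, *m*, is 12 (an even split), with an 8/17 split as an alternative. Fiber variance is set to 1. Subject-by-time variance *r* is 0, 0.01, 0.05 or 0.10 of it. The design is balanced.

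**Formulas for group-by-time.**
- True variance of the contrast: 4(1/m + r)/12.
- Expected subject-by-time mean square: 1 + mr, on 24 − 2 = 22 df.
- Within-biopsy mean square: expectation 1, on 48(m − 1) df.
- The subject-intercept model pools the two: [22(1 + mr) + 48(m − 1)] / [22 + 48(m − 1)].
- True SE divided by the SE the model uses: R = √[(1 + mr)/pooled].
- Type I error ≈ 2[1 − Φ(1.96/R)].

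**Worked case, m = 12, r = 0.05.** 1 + mr = 1.6. Pooled = (22 × 1.6 + 528)/550 = 1.024. R = √(1.6/1.024) = 1.25. Type I error ≈ 2[1 − Φ(1.568)] = 11.7%.

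**Simulated type I error, 1,000,000 draws per cell:**

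| Analysis | r = 0 | 0.01 | 0.05 | 0.10 |
|---|---|---|---|---|
| Subject intercept only, m = 12 | 5% | 6% | 12% | 18% |
| Subject intercept only, m = 8 (rarer type) | 5% | 6% | 9% | 13% |
| Subject intercept only, m = 17 (commoner type) | 5% | 7% | 14% | 22% |
| Patient means, m = 12 | 5% | 5% | 5% | 5% |
| Biopsy random effect, 22 df, m = 12 | 3.1% | 3.7% | 4.7% | 5.0% |

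At m = 12 the error reaches 10% at r = 0.038. The reported confidence interval is on average 96, 91, 77 and 66% of the patient-level width across the four ratios. Pooling all 25 fibers gives 5, 8, 19 and 28%, but this is the least applicable case: an unmodelled difference between fiber types would add to the fiber variance and lower *r*.

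**Alternative contrast.** For the post-intervention group difference in the same model, the true variance is 2(s + r + 1/m)/12, where *s* is the subject variance. With s = 0.1–0.4, r = 0.01–0.10 and 22 df, type I error is 4.8–6.7% at m = 12 and 5.0–7.5% at m = 25.

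**Check with fitted models.** Small REML runs on null data (m = 12, s = 0.2) agree within Monte Carlo error of about 1–4 points. The subject-intercept model rejected in 16% of 134 datasets at r = 0.10, 8.5% of 106 at r = 0.05 and 6% of 48 at r = 0. The biopsy random effect rejected in 4.5, 1.9 and 4%.

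**The case against.** The strongest reply is that the plan may already contain the missing term. Calling time a within-subject effect is repeated-measures language, and the usual error for group-by-time in that setting is subject-by-time. Mentioning one random effect does not exclude others, and the cited study may define a fuller model. This cannot be ruled out. However, the random effect is described in words, and those words stop at fibers within subjects. No section names a biopsy term, a covariance structure for time or a degrees-of-freedom method.

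Second, the Aim 1 wording speaks of differences versus controls, and the phrase about detecting changes concerns mitochondrial content. If the test is the post-intervention difference, the problem nearly disappears. That stands, and it is why the finding is conditional. Even so, a reader should not have to guess the contrast.

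Third, the biopsy-level variance is unknown. At zero the 5% level holds, and at a ratio of 0.01 the error is only about 6%. That also stands: the level is not assured, but inflation has not been shown.

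Finally, this is a proof-of-principle study. That limits the consequences, but its results are meant to support larger trials.

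**Conclusion.** The concern holds as a conditional statement. Fitted as written and tested on group-by-time, the model does not assure the 5% level for fiber tension and velocity. With 12 fibers per type the true level runs from 5% to 18% as the subject-by-time variance goes from 0 to 0.10 of the fiber variance. The reported intervals shrink accordingly, to as little as 66% of the patient-level width. These sizes rest on assumed variance ratios, an assumed split of fibers by type and a balanced design. No size is claimed for CSA or mitochondrial content, because the documents give no reading count for them. As the text stands, a reader cannot tell which contrast is tested or against which error term. This should be fixed before analysis.

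**What to change.** State in the Statistical Analysis Plan:

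1. The treatment effect is the group-by-time contrast.
2. For outcomes with several readings per biopsy, either add a random effect for biopsy within subject (subject-by-time), tested with Satterthwaite or Kenward-Roger degrees of freedom (about 22), or analyse one mean per patient, biopsy and fiber type.
3. Which outcomes enter as a single value per biopsy.

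If the cited method already contains the biopsy-level term, write it out. Separate fits by fiber type are optional.

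The cost is a few sentences and no extra data. Intervals become wider but valid. This is a real loss only if the subject-by-time variance is zero. In that case the interval is about 4% wider with patient means and about 11% wider with the biopsy random effect, and 90% power becomes about 87% or 85%. The biopsy random effect is slightly conservative when the biopsy variance is near zero.
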